### **B. Specific Objectives**

#### **a. Primary Objectives**

- i. To determine the average CD4 value in immunological non responder HIV patients treated with Probiotic compared to placebo
- ii. To determine the average T helper 17 value in immunological non responder HIV patients treated with Probiotic compared to placebo
- iii. To determine the average 16S rDNA value in immunological non responder HIV patients treated with Probiotic compared to placebo
- iv. To determine the fecal calprotectin value in immunological non responder HIV patients treated with Probiotic compared to placebo

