### C. Study Population

1. Targeted Population: HIV patients with Immunological Non-responder condition in Indonesia
2. Sample: HIV patients with Immunological Non-responder condition in Indonesia
3. Inclusion Criteria:
  - a. HIV positive patients aged 18-55 years old
  - b. had already treated with first line Highly Active Anti Retroviral Therapy for at least 6 months
  - c. had CD4 level of 200-410 cell/ $\mu$ L
  - d. undetectable Viral Load (<34 copies/ml blood)
  - e. agreed to participate in the study and signed the informed consent
4. Exclusion Criteria:
  - a. Pregnant patients
  - b. Lactating patients
  - c. Known *Lactobacillus* allergy
  - d. Body Mass Index (BMI) <16 kg/m^2
  - e. Under Tuberculosis treatment or other acute illness, acute diarrhea,
  - f. routinely taking selenium containing vitamin in last 1 month,
  - g. routinely consuming probiotics containing product in last 1 month
5. Estimation Sample Size: 80 samples. Which will be divided into two groups equally.
6. Study Procedure

[figure not shown]
Eligible patients will be approached to be enrolled in the clinical trial. Informed consent will be obtained. Patients will be randomized and divided into two groups, intervention and placebo group. Intervention group will receive Probiotics (Chewable tablet) containing *Lactobacillus plantarum*, *Streptococcus thermophiles*, *Bifidobacterium bifidum* once daily. While, Placebo group will receive placebo which had identical shape, flavor, and smell as the interventional drug.

Intervention will be held for 12 weeks. CD4, Th17, 16S Ribosomal RNA, and fecal calprotectin level will be checked at the 0 week and repeated after 12 weeks of intervention. Self administered HIV Symptoms Index questionnaire will be filled by the respondent on 0,4,8,12 weeks of intervention. Food frequency questionnaire will be filled by the respondents with the help of nutritionist on 0,4,8,12 weeks of intervention.

7. Side effects

All side effects that may arise and related to probiotics intake will be assessed and reported. Appropriate medical advice will be provided.

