#### IV. Statistical Analysis Plan

All Data will be analyzed using SPSS 24.0 (SPSS) for Windows. Laboratory parameters will be compared between two different times and also compared between two groups by using paired and independent t test (if normally distributed) or using Wilcoxon and Mann Whitney (if not normally distributed). Statistically significance was determined by p value <0.05. Intention to Treat analysis will be used. HIV symptom index and food frequency will be reported descriptively.

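### Intention to treat is named without a rule for missing week-12 values, so by default the four primary comparisons use only patients with an observed week-12 value

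*Combined protocol and SAP*

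**What the plan says.** Section IV (Statistical Analysis Plan) compares the laboratory markers between times and between groups "by using paired and independent t test (if normally distributed) or using Wilcoxon and Mann Whitney (if not normally distributed"). It then adds "Intention to Treat analysis will be used". It does not define the intention-to-treat set, and it gives no imputation method, missing-data assumption or sensitivity analysis.

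Section II.B.a lists four primary objectives, all between-arm comparisons of a laboratory marker: CD4, Th17, 16S rDNA and fecal calprotectin. Under Study Procedure (Section III.C, item 6) these markers "will be checked at the 0 week and repeated after 12 weeks of intervention", so each has one post-baseline value. The same item schedules one repeated measure between those visits that bears on patients' condition: "Self administered HIV Symptoms Index questionnaire will be filled by the respondent on 0,4,8,12 weeks of intervention".

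Section III.C, item 5, sets 80 patients in two equal groups. Section III.B recruits until the minimum sample size is reached. Neither states a dropout allowance or says whether 80 counts patients randomised or patients with a week-12 result.

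**The concern.** Each named test needs a week-12 value. Unless an imputation step is added, the software drops patients who lack one, and the result is an observed-case analysis reported as intention to treat. A reader of the report could not tell the difference.

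Two things are at stake. First, if patients leave for reasons related to a marker, and this differs between arms, the arms compared are no longer the arms randomised. Second, because the plan is silent, the handling (exclude, carry baseline forward, impute) can be chosen after the data are seen, and the choices can give different answers. With 40 per arm, a few patients matter.

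**Working it through.** **Inputs from the documents.** 80 patients in two equal groups, so 80/2 = 40 per arm (Section III.C, item 5). Significance at p < 0.05 (Section IV), taken as two-sided because sidedness is not stated. One post-baseline value per marker (Section III.C, item 6).

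**Not in the documents, so assumed.** Dropout rates, how dropouts differ from those who stay, power of 80%, a week 0 to week 12 correlation of 0.6, and equal SDs at both times.

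**1. The plan's own figure.** The 80 cannot be reproduced, because no effect size, SD, power or dropout rate is given. Working backwards, 40 per arm at 80% power detects (1.960 + 0.842) × √(2/40) = 0.63 SD. That is the yardstick below.

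**2. Bias of the observed-case comparison when there is no true effect.** Let d be the proportion missing in an arm and g the mean of the missing minus the mean of the observed, in SD. If the whole arm has mean 0, the observed patients have mean −d·g. With A the probiotic arm and B placebo:

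- bias = −dA·gA + dB·gB
- SE = √[1/(40(1−dA)) + 1/(40(1−dB))]
- type I error = 1 − Φ(1.96 − bias/SE) + Φ(−1.96 − bias/SE)

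Example, dropout 20% and 10%, g = −1 in both: bias = 0.20 − 0.10 = 0.10; SE = √(1/32 + 1/36) = 0.243; type I error = 7.0%.

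| Dropout A / B | gA / gB | Bias (SD) | Type I error |
|---|---|---|---|
| 20% / 20% | −1 / −1 | 0 | 5.0% |
| 5% / 5% | −1 / 0 | 0.05 | 5.5% |
| 10% / 10% | −1 / 0 | 0.10 | 7.1% |
| 20% / 20% | −1 / 0 | 0.20 | 12.6% |
| 20% / 10% | −0.5 / −0.5 | 0.05 | 5.5% |
| 20% / 10% | −1 / −1 | 0.10 | 7.0% |
| 20% / 10% | −1 / 0 | 0.20 | 13.1% |

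Equal rates with equal selection give no bias. Bias needs a difference between arms.

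**3. A ceiling when dropout depends on baseline only.** If exactly the worst 20% and the worst 10% at baseline leave, the mean baseline of those remaining rises by 0.350 and 0.195 SD. The bias in week-12 values is then 0.6 × (0.350 − 0.195) = 0.093 SD. A larger bias from baseline-driven dropout at these rates needs selection that differs by arm. With selection in the 20% arm alone, the ceiling is 0.6 × 0.350 = 0.21 SD. A milder common selection (odds ratio 2.7 per baseline SD) gives 0.05 SD and about 5.5%.

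**4. Simulation at 20% against 10% dropout, 40 per arm, correlation 0.6, t test on week-12 values.** Same selection in both arms: bias 0.04 to 0.07 SD, type I error 5.1 to 5.7%. Selection in one arm only: 0.14 to 0.18 SD, 8.4 to 11.2%. Against 0.63 SD, that is 6 to 11% and 22 to 29% of the detectable difference.

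**5. What the remedies recover.** When dropout depends on baseline, regression of week 12 on arm and week 0 in observed cases brings bias within 0.01 SD and type I error to about 5%. When dropout also depends on interim symptoms, and symptoms are assumed to correlate 0.4 with the part of the outcome that baseline does not explain, that regression keeps about 0.02 to 0.07 SD. Multiple imputation using symptoms then stays within 0.01 SD, with type I error of 4.3 to 5.1%.

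**6. Power.** Losing patients lowers power at about 0.63 SD from 80% (40 per arm) to 76% (36) and 70 to 71% (32). Baseline adjustment shrinks the residual SD to √(1 − 0.6²) = 0.8. The same difference then counts as 0.634/0.8 = 0.79 residual SD, and power without dropout is about 94%.

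**The case against.** The strongest reply is that the plan is silent rather than wrong. A t or rank test runs on whatever data set it is given, including an imputed one, and nothing in Section IV excludes imputation. A patient who stops the tablets but gives a week-12 sample is still analysed. A reader might infer that the plan prescribes a completer analysis; the text does not say so. What stands is that observed cases are the default when no other rule is written.

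A reader might also infer that any selective dropout biases all four primary comparisons and pushes type I error above 5%. The documents do not support that. Equal rates and equal selection leave the comparison unbiased under no effect, and a marker unrelated to the reason for dropout is unaffected. The placebo matches the product in shape, flavour and smell, which gives some reason to expect similar dropout, though it does not rule out differences arising from effects or side effects. The larger figures above come from selection confined to one arm, which is an assumption.

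The figures are also for week-12 values. Section IV does not say whether the independent test uses those or changes from baseline. For change scores the bias differs and can have the opposite sign.

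Finally, the case for imputation rests on a link between the HIV Symptom Index and the laboratory markers that the documents do not show; Section II.B.b uses the index for quality of life. This objection stands and limits what imputation can be said to add. It does not touch baseline adjustment.

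Nothing in the documents says that dropouts would be replaced. The open question is only what the 80 counts.

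**Conclusion.** The gap is real, and its consequence is conditional. The plan names intention to treat without carrying it through to patients who lack a week-12 value. The resulting comparison of a marker is biased only where missingness related to that marker differs between arms. The size cannot be known from the documents. It is negligible at about 5% dropout, modest at 20% against 10% with common selection, and material only with selection largely in one arm. All of these figures rest on the assumed dropout and selection patterns, and the simulated ones also on a correlation of 0.6. The plan should be amended, because the main remedy uses data already collected and improves precision even if nobody drops out.

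**What to change.** In Section IV:

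- Define the primary analysis set as all randomised patients in their assigned arm.
- Make the primary between-arm comparison of each marker a regression of the week-12 value on arm and the week-0 value, on a log or rank scale if the marker is not normal.
- Prespecify multiple imputation of missing week-12 values from arm, the four week-0 markers and the HIV Symptom Index at weeks 0, 4 and 8.
- Report the observed-case baseline-adjusted result and a delta-shift of the imputed values as sensitivity analyses.

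In Section III, state that the planned week-12 sample is sought from every randomised patient, including those who stop the study product, and that 80 counts patients randomised.

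The cost is protocol and SAP wording and a little more analysis work, with no added visits, assays or patients. The primary result would rest on a stated missing-at-random assumption, which the delta-shift examines. Most of the benefit comes from baseline adjustment. The further gain from imputation is small and depends on how well symptoms predict the markers.

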#### **b. Secondary Objectives**

To determine the effect of Probiotic supplementation towards quality of life improvement in immunological immunological non responder HIV patients, using HIV symptom index.

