## **III. Methods**

### **A. Study Design**

This study is double-blind randomized control trial design

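### The only secondary objective asks for the probiotic's effect on quality of life, but the SAP plans no between-arm estimate, analysis visit or interval for the HIV symptom index

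*Combined protocol and SAP*

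**What the plan says.** Section II.B.b (Secondary Objectives) lists a single secondary objective: "To determine the effect of Probiotic supplementation towards quality of life improvement", with the HIV symptom index as the instrument. Section III.A gives the design: "This study is double-blind randomized control trial design". Section III.C.6 describes the placebo arm and the collection schedule: "Self administered HIV Symptoms Index questionnaire will be filled by the respondent on 0,4,8,12 weeks of intervention". Section III.C.5 gives the size: "Estimation Sample Size: 80 samples. Which will be divided into two groups equally".

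The Statistical Analysis Plan (section IV) assigns comparative methods to one class of outcome only: "Laboratory parameters will be compared between two different times and also compared between two groups". It deals with the index separately: "HIV symptom index and food frequency will be reported descriptively". It also states "Intention to Treat analysis will be used", but does not say what this means for a missing questionnaire. No section gives a scoring rule for the index.

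**The concern.** In a randomised placebo-controlled trial, an effect of treatment is a contrast between the arms. The objective asks for that contrast and the analysis plan does not supply it. Summaries of the index, even if given by arm (the SAP does not say they will be), would show a direction. They would not show how large a difference chance alone could produce.

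The missing analysis visit also matters. The index has three post-baseline visits (weeks 4, 8 and 12), whereas the laboratory measures have one (week 12). If the report goes on to state an effect on quality of life, nothing in the plan fixes which visit it rests on, so the visit could be chosen after the data are seen. That is a possibility the plan leaves open; nothing shows that it will happen. The primary laboratory conclusions are not touched.

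**Working it through.** **Reading the sections together**

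| Element | HIV symptom index | Laboratory parameters |
|---|---|---|
| Objective | Effect of probiotic (II.B.b) | Values under probiotic compared with placebo (II.B.a) |
| Collected | Weeks 0, 4, 8, 12 (III.C.6) | Weeks 0 and 12 (III.C.6) |
| Between-arm method | None (IV) | Independent t or Mann-Whitney (IV) |
| Analysis visit | Not named | Week 12 is the only post-baseline visit |
| Confidence interval | None | None |

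The general SAP statements on the 0.05 threshold and on intention to treat do not fill the gap, because neither supplies a comparison for the index.

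**Uncertainty that would go unreported (illustration)**

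The plan has no figure of its own to reproduce: it gives no SD, effect size, power or dropout rate for any endpoint. From the documents: 80 participants split equally, so n = 40 per arm. Assumed: a week 0 to week 12 correlation r of 0.4–0.7, and 0%, 10% or 20% of week-12 scores missing (40, 36 or 32 per arm). Results are in units of the within-arm SD.

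- Unadjusted 95% half-width = t(0.975, 2n−2) × √(2/n). For n = 40: 1.991 × 0.2236 = 0.445.
- Baseline-adjusted (ANCOVA) half-width = t(0.975, 2n−3) × √((1−r²) × 2/n).

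| n per arm | Unadjusted | r = 0.4 | r = 0.5 | r = 0.6 | r = 0.7 |
|---|---|---|---|---|---|
| 40 | 0.445 | 0.408 | 0.386 | 0.356 | 0.318 |
| 36 | 0.470 | 0.431 | 0.407 | 0.376 | 0.336 |
| 32 | 0.500 | 0.458 | 0.433 | 0.400 | 0.357 |

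Baseline adjustment narrows the interval by about 1 − √(1−r²): 8.3% at r = 0.4 and 28.6% at r = 0.7.

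With 40 per arm, an unadjusted observed difference of up to about 0.44 SD would still have a 95% CI that includes zero. A table of means or percentages would not reveal this.

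**Does the interval hold up?** Simulation with normal scores (4,000 runs per setting) gave mean ANCOVA half-widths of 0.409 and 0.319 at n = 40, and 0.460 and 0.358 at n = 32, for r = 0.4 and 0.7. Coverage was 0.950–0.954. With a right-skewed score (lognormal, log-SD 0.8, no true effect), coverage was 0.950–0.953 at both sizes. In that assumed case, skew does not break the interval.

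**The case against.** The strongest reply is that the SAP made a choice: it names the index and gives it a method. Descriptive reporting of a secondary questionnaire in an 80-person trial is defensible. Since no test of the index is planned, no selective significance claim follows from the plan itself; the harm arises only if the authors go beyond it. Rewording one sentence would remove the mismatch. ANCOVA with imputation is one option among several, and it would give the secondary questionnaire a more elaborate analysis than the primary laboratory endpoints receive. The absence of confidence intervals and of a missing-data rule runs through the whole plan and is not peculiar to the index. The SD-unit figures show what precision is available, not an error the plan makes.

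Much of this stands. Descriptive reporting is legitimate in itself, and rewording the objective is an acceptable remedy. By-arm summaries are a natural reading of the SAP, although it does not say so. A repeated-measures model would also close the gap. The plan-wide omissions should not be counted as extra weight here.

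It does not remove the point. While the objective is worded as an effect, the plan does not deliver what it asks for. The laboratory endpoints at least receive a two-group test; the index receives none.

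**Conclusion.** The concern holds. Following the SAP as written gives no specified between-arm estimate, analysis visit or interval for the trial's only secondary objective. This conclusion rests on the text alone and needs no assumption.

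The size is illustrative: a 95% half-width of 0.445 SD unadjusted with complete data, rising to 0.500 SD if 20% of week-12 scores are missing, and between 0.46 and 0.32 SD with baseline adjustment across the assumed correlations and missingness. Only the 40 per arm comes from the documents. They give no SD or meaningful difference for the index, so these figures cannot be converted to points on its scale.

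The plan should be changed on this point, but no primary conclusion depends on it. The missing scoring and missing-score rules are details to add alongside; the case does not rest on them.

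**What to change.** In section IV, keep descriptive summaries of the index by arm at weeks 0, 4, 8 and 12, and add one prespecified estimate before unblinded data are examined: the between-arm difference in index score at week 12, adjusted for the week-0 score by ANCOVA, with a 95% CI, in the intention-to-treat set. State how the index is scored. State how a missing week-12 score is handled, for example by multiple imputation from arm and the week 0, 4 and 8 scores, and report the number missing by arm. Label the result secondary and supportive, with no significance claim.

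If the sponsor prefers a purely descriptive analysis, reword the objective in II.B.b as descriptive and draw no effect conclusion. Food frequency can stay descriptive either way.

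Cost: a few lines of SAP text, two rules and one model, with no new data collection; the rewording route costs one sentence. The downside of the first route is one more inferential result in a plan that already has four primary objectives, a 0.05 threshold and no multiplicity rule. Giving an estimate and interval without a significance claim limits that problem but does not control the error rate.
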